### 8.7.11 Functional Ambulation Categories

Functional ambulation categories (FAC) (105) is a useful scale to assess gait in patients with foot drop. It is a six point scale, that is used in stroke literature (99, 106-109) and can help determine how much assistance a patient requires. A  $\text{FAC} \geq 3$  has been considered a surrogate of general walk ability in assessing mobility in stroke patients (108, 110). Mehrholz (111) showed a strong correlation between FAC and commonly used indicators of progress in gait performance. A  $\text{FAC} \geq 4$  could predict community ambulation with high sensitivity and specificity. Lord (99) assessed mobility in stroke patients. The highest

FAC was achieved by 72.3% of all 130 subjects and median FAC was 5. Again, extrapolation of these data is not ideal. However, taking all data into account, **good outcome correlates with a FAC of 5**.

Gait assessment through functional ambulation score is not considered standard of care. The FAC will be determined by the outcome assessor at baseline, 6 weeks, 3 months, 6 months, 9 months and 18 months after randomization.

Functional ambulation categories (FAC)		
FAC 0	Nonfunctional	
 
- No ambulation
 
- Ambulation only in parallel bars
 
- Requires supervision or physical assistance from > 1 person
 

FAC 1	Dependent (level II) MCID	
 
- Requires manual contact of one person during ambulation on level surfaces
 
- Manual contact is continuous and necessary to support body weight and/or to maintain balance and coordination
 

FAC 2	Dependent (level I)	
 
- Requires manual contact of one person during ambulation on level surfaces
 
- Manual contact is continuous or intermittent light touch to maintain balance/coordination
 

FAC 3	Dependent, supervision	
 
- Ambulation occurs on level surfaces without manual contact of another person
 
- Requires stand-by guarding of one person because of the need for verbal guidance or poor judgement or questionable cardiac status
 

FAC 4	Independent, level surfaces only	
 
- Ambulation is independent on level surfaces
 
- Requires supervision/physical assistance to walk stairs, inclinations or non-level surfaces
 

FAC 5	Independent, level and non-level surfaces	Ambulation is independent on non-level surfaces, inclinations and stairs.

#### 8.7.12 Quality of life: the EQ5D-5L questionnaire

We will use the validated and commonly used EQ5D-5L (5 Level EUROQoL – 5 Dimensions) questionnaires to assess patient reported outcome measures (PROM). The EQ5D-5L questionnaires is attached to the protocol in Appendix 8. Assessing quality of life through the EQ5D-5L questionnaire is not considered standard of care. The questionnaire will be available as an online survey (REDCap) for the patients. If patients forget or don't want to use the online system, the outcome assessor will provide the questionnaire at the randomization visit, at 10 days (surgical group), 6 weeks, 3 months, 6 months, 9 months and 18 months after randomization and data will be collected in the eCRF. The treating physician

will provide the EQ5D-5L questionnaire at 10 days (surgical group) if a patient does not use the online system. This can only be done by the treating physician to guarantee blinding.

The EQ-5D 5L is a generic measure of health-related quality of life developed by the EuroQol Group. It is a validated measurement of quality of life widely used in different pathologies. The questionnaire is made up of two parts. The first part is descriptive and uses five different dimensions to score quality of life. These five dimensions are mobility, self-care, activities of the daily life, pain/discomfort and anxiety/depression. There are five different answer possibilities within each dimension, i.e. "no problem", "slight problem", "moderate problem", "severe problem" and "unable to". This renders 3125 different answer possibilities. The second part uses a visual analogue scale (VAS) to score the current health status of the patient, ranging from zero to one hundred. Zero corresponds to death and one hundred corresponds to a (subjective) perfect health status.

N.B.: Based on patient feedback throughout the pilot study, the SF-36 questionnaire will no longer be used. Patients experienced the questionnaire as too extensive. Furthermore, quality of life questionnaires were among the least popular trial assessments.

#### **8.7.13 Surgical Complications**

Overall, neurolysis of the peroneal nerve is considered a low-risk surgery (113). Surgical complications will be assessed by the treating physician at 10 days and 6 weeks. This is considered standard of care. We will use a list of possible complications based on the available literature (1, 3, 43, 44, 47, 48, 50, 51, 55) and our own experience. In this way, surgical complications can be uniformly scored throughout all participating centers. Unforeseen complications will be recorded as free-text. After cross-over, surgical complications will be assessed by the outcome assessor at the extended follow-up visit (18 months).

List of predefined possible surgical complications:

Impaired/prolonged wound healing
Wound infection with need for antibiotics
Wound dehiscence without need for revision surgery
Wound dehiscence with need for revision surgery
Postoperative hematoma without need for revision surgery
Postoperative hematoma with need for revision surgery
(partial) Transection of peroneal nerve with new sensory deficit
(partial) Transection of peroneal nerve with new motor deficit
Persisting pain in the operated area
Development of complex regional pain syndrome

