## 2 RATIONALE

The rationale for this study is to explore whether a surgical approach to peroneal nerve entrapment is warranted i.e. **does a foot drop, caused by peroneal nerve entrapment, recover faster and better after surgical release?** This question is relevant, given the fact that the actual treatment strategy varies greatly between and even within different centers, depending on the consulting physician.

Since peroneal nerve entrapment represents one of the most common entrapments, and no practice guidelines exist on its preferred treatment, this prospective study will provide important outcome data after conservative treatment (current data very limited), as well as surgical treatment (current data very biased, retrospective in nature and uncontrolled). The impact on quality of life will be assessed and the complications (surgical, chronic pain, sensory changes, ...) of both treatments will be recorded. These data will define future treatment guidelines for this mononeuropathy and is thus relevant for all physicians treating entrapment neuropathies (neurology, neurosurgery, physical medicine, orthopaedic surgery, ...).

There is indeed insufficient data in the available literature to make any recommendations. No studies have compared surgical versus conservative treatment in a prospective manner and currently no guidelines are available. Even data on the prevalence and the spontaneous evolution of peroneal neuropathy are virtually non-existent.

The lack of prospective studies on this topic is remarkable since most patient series on both the conservative and surgical treatment are retrospective in nature. Most patient series are very heterogeneous given the fact that patients with peroneal nerve damage due to different causes were included, which makes it difficult to draw conclusions on the clinical management. Based on the current literature, the percentage of patients with good outcome after conservative treatment varies between 53% and 100% (9, 22, 24, 28, 36-40). Data concerning the spontaneous evolution of peroneal nerve entrapment (without any intervention) is almost absent, except for 15 patients (28, 41). Furthermore, studies discussing prevalence, report contrasting percentages (7-9).

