##### Other Secondary outcomes

1. **Ankle dorsiflexion strength:** measured by the MRC-score and isometric dynamometry at 10 days, 6 weeks, 3 months, 6 months, 9 months and 18 months after randomization. Ankle dorsiflexion strength will also be assessed after 10 days in the surgical arm of the trial.
2. **Gait assessment** at 6 weeks, 3 months, 6 months, 9 months and 18 months after randomization with
  - a. Functional ambulation categories, Stanmore questionnaire
  - b. Gait speed during the 10-meter walk test
  - c. The proportion of patients in both groups who reach minimal normal age- and sex-specific reference values for 6MWD, 9 months after randomization.
  - d. Difference in distance covered in meters during the six-minute walk test between baseline and 6 weeks, 3 months, 6 months and 18 months after randomization
3. **Complications and neurological deficits :**
  - a. Motor changes including MRC-score for ankle eversion and hallux extension at 6 weeks, 3 months, 6 months, 9 months and 18 months after randomization. Motor function will also be assessed after 10 days in the surgical arm of the trial.
  - b. Sensory changes at 6 weeks, 3 months, 6 months, 9 months and 18 months after randomization. Sensory changes will also be assessed after 10 days in the surgical arm of the trial.
  - c. Surgical complications at 10 days, 6 weeks and 18 months after surgery: a list of possible complications is composed to score in a uniform way in all centers.
4. **Health-economic assessment:**
  - a. Work productivity and Activity Impairment Questionnaire at 6 weeks and 6 months after randomization.
  - b. Return to work at 6 weeks after randomization.
5. **Electrodiagnostics (EDX)** at 3 months and 9 months after randomization.
6. **Patient-reported outcome measures:** health-related quality of life (EQ5D-5L) at 6 weeks, 3 months, 6 months, 9 months and 18 months after randomization. Patient-reported outcome measurements will also be assessed after 10 days in the surgical arm of the trial.

For all secondary endpoints, baseline measurements will be obtained if applicable.

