### 8.4 Blinding

Blinding of trial participants and care providers is not possible because of obvious differences between both treatment groups: one group will be surgically treated whereas the other group will receive maximal conservative treatment until the primary endpoint is assessed. However, the clinical investigator in the foot drop trial (= outcome assessor) can be blinded to treatment. All participants will be asked to wear long trousers to cover a potential scar at the level of the knee. Furthermore, all patients will be asked to apply a bandage at the site of the operation (or the site of entrapment if there was no operation). Participants are not allowed to discuss their treatment with the outcome assessor. A preassessment contact between the patient and an unblinded member should be organized prior to the study assessments, to remind and instruct patients of the blinding precautionary measures.

Patients in the surgical arm of the trial will be evaluated after 10 days. A postoperative control is considered standard of care. Assessments cannot be performed by the outcome assessor at this stage, as this will cause unblinding.

Since all health care providers have access to the electronic health record, measures should be taken to prevent unblinding of the outcome assessors. Several precautions should be considered:

- Data of assessments will be documented on a separate worksheet, outside the electronic health record so that there will be no need to access the electronic health record.
- If the outcome assessor thinks the electronic health record should be accessed, the treating physician should be consulted. Since the treating physician is not blinded, he/she can access the electronic health record if deemed necessary.

To avoid errors, the outcome assessor must be aware of the identity of the patient during the assessments. Therefore, anonymization during assessment is not possible.

Blinding the outcome assessor will create the opportunity to make an objective assessment of primary and (key) secondary outcome parameters, without increasing the risk of bias.

Until the time of unblinding for final data analysis, the randomization list is kept strictly confidential. The randomization list is accessible only by the REDCap data manager to prevent further selection bias. The statistician should neither have access to randomized treatments (or randomization list) nor even to the full database until the database has been locked for analysis.

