chronic pain and possible skin problems due to sensory and autonomic deficits, we believe that this condition will have an important impact on quality of life. In addition to quality of life measures, the work productivity and impairment questionnaire (WPAI) will be used to assess employment and professional productivity. The WPAI will be collected at baseline, 6 weeks and 6 months. The professional occupation of patients will be collected as baseline data. Return to work will be assessed six weeks after randomization. We expect patients to be able to return to work after improvement (of recovery) of foot drop. Relapse of foot drop is not expected in the majority of cases (see also Section 8.7.16).

The proposed trial will provide the ideal opportunity to collect data about quality of life, surgical complications, employment and professional productivity in patients with a foot drop due to peroneal nerve entrapment. In addition, these data will provide further insights into the quality of life of people with a foot drop resulting from other aetiologies (such as lumbar disc herniation), and even about patients with other entrapment neuropathies.

The economic evaluation will be conducted from a healthcare payer (base case) and societal perspective. The aim of the economic evaluation is to measure, value and analyse total costs of patients in both groups and to relate the difference in costs between the two treatment groups to the difference in clinical effects. The time horizon of the economic evaluation is 18 months, after collection of all clinical data that can be used for the cost evaluation of the intervention. Sensitivity analysis will be performed to assess the robustness of the results using different assumptions regarding costs and effects.

Effect measures in the economic evaluation will be calculated by the available QOL-questionnaires (EQ-5D 5L at baseline, 6 weeks, 3 months, 6 months, 9 months and 18 months). EQ-5D 5L is a sensitive QOL instrument in this trial, since mobility is one of the five dimensions of the EQ-5D 5L questionnaire. Therefore, we expect differences in outcome to be reflected in differences in EQ-5D 5L. EQ-5D 5L value sets are expected to be available at the end of the trial. If not, the EQ-5D-5L Crosswalk Index Value Calculator can be used. We expect to see a higher QOL for the surgical management of the foot drop.

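### Persisting pain and complex regional pain syndrome are solicited as complications only from operated patients, although the Rationale says complications including chronic pain will be recorded for both treatments

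*Protocol*

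**What the plan says.** Section 2 (Rationale) states the intention for both arms: "the complications (surgical, chronic pain, sensory changes, ...) of both treatments will be recorded". The Trial Summary lists complications and neurological deficits as a secondary endpoint at 10 days, 6 weeks, and 3, 6, 9 and 18 months. It restricts only the 10-day visit to the surgical group.

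Section 4.3.2 divides that endpoint into motor changes, sensory changes and surgical complications. Motor and sensory changes are followed in both arms. The third part is timed from the operation: "Surgical complications at 10 days, 6 weeks and 18 months after surgery".

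Section 8.7.13 holds the predefined list and says who completes it: "Surgical complications will be assessed by the treating physician at 10 days and 6 weeks". Most items concern the wound, haematoma or nerve transection. The last two are "Persisting pain in the operated area" and "Development of complex regional pain syndrome". A patient randomised to conservative treatment is assessed with the list only after crossing over, at the 18-month visit.

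Section 11.5 expects people with a permanent motor deficit to suffer "chronic pain and possible skin problems due to sensory and autonomic deficits", and does not confine this to operated patients.

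**The concern.** Wound problems, haematoma and transection can occur only after surgery, so a surgery-only list suits them. Pain around the knee or lower leg and CRPS are different, because a patient with a lasting palsy who has not been operated on may have either. The protocol's own expectation of chronic pain in section 11.5 means that absence in the conservative arm cannot be taken for granted.

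As scheduled, an operated patient is asked about these two items at 10 days and 6 weeks. A conservative patient is not asked about them as complications at all before cross-over. Any table setting complication counts side by side would compare a solicited count with one that was not solicited, and the difference would tend to count against surgery whatever the true rates. A later analysis plan cannot repair this, because the missing answers would never have been collected.

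**Working it through.** The plan gives no figure for pain or CRPS, so there is none to reproduce. The check is mainly a comparison of sections, followed by an illustration on assumed rates.

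**Step 1. Which routes could capture these harms in a conservative patient before cross-over?**

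| Source | Reaches conservative patients? | Asks about pain? | Identifies CRPS? |
|---|---|---|---|
| Surgical complication list (8.7.13; 4.3.2 item 3c) | No | Yes, in the operated area | Yes |
| Standard assessments at every visit (8.7; Appendix 4) | Yes | No | No |
| Stanmore questionnaire (8.7.7) | Yes: randomisation, 6 weeks, 3, 6, 9, 18 months, by the blinded assessor | Yes, 15 of 100 points | No |
| EQ-5D-5L (8.7.12; Appendix 8) | Yes, at the same visits | Yes, general pain or discomfort | No |
| Adverse events (8.8; 10.2) | Yes | Not prompted | Only if reported |

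**Step 2. How well do the shared routes replace the list?**

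- Stanmore gives its full 15 pain points both to a patient without pain and to one whose pain has not worsened. Unchanged, persisting pain can therefore score the same as none.
- The EQ-5D item asks about pain in general on that day and is not tied to the affected leg.
- Section 10.2 relies on participants reporting events that they connect with the study intervention. Someone whose pain comes from an unrelieved palsy has little reason to report it in that way.
- CRPS is solicited on the surgical list and nowhere else.

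**Step 3. What could unequal ascertainment do to a comparison of counts?**

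Inputs: 91 patients per arm (section 11.1: 172 / 0.95 = 181.05, made up to 182, so 182 / 2 = 91). Assumptions: the same true rate p in both arms; every surgical patient is operated on and every event is captured by the list; no conservative event is captured by it.

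Expected list counts are 91 × p against 0. For k events against none, the two-sided Fisher exact p-value is 2 × C(91,k) / C(182,k). This is 0.059 for k = 5 and 0.029 for k = 6, so six against none is enough for p < 0.05. The chance of a false signal is then P(X ≥ 6) with X ~ Binomial(91, p).

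| Assumed true rate, both arms | Expected count, surgery | Expected count, conservative | Chance of p < 0.05, one arm asked | Chance of p < 0.05, both arms asked |
|---|---|---|---|---|
| 2% | 1.8 | 0 | 1% | 0.4% |
| 5% | 4.6 | 0 | 30% | 1.9% |
| 10% | 9.1 | 0 | 90% | 2.7% |
| 20% | 18.2 | 0 | about 100% | 3.3% |

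The rates are assumed. The protocol states no between-arm test of the list, so the table shows what such a comparison would risk and does not predict a planned result.

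**The case against.** The strongest reply is that pain is already asked about in both arms. Before month 9 a conservative patient meets the Stanmore pain section and the EQ-5D pain item at three post-randomisation visits (6 weeks, 3 and 6 months), and again at 9 and 18 months. Both instruments are named secondary outcomes, and a blinded assessor scores Stanmore. Section 2 promises recording without naming an instrument. The pain item on the list is worded for an operated area, and item 3c is timed from surgery, so the list can be read as a description of operated patients only. The analysis of other secondary endpoints is left to a plan that is not shown.

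Much of this stands. A reader might infer that these harms can only ever be counted against surgery, or that control patients are never asked about pain. The documents do not support that: pain severity can be compared between arms, and CRPS in a conservative patient could still be reported as an adverse event. A reader might also multiply the 30 to 35% cited in section 11.5 by 91 to size the problem. That percentage is permanent motor weakness when the neuropathy is not treated properly. It is not a rate of pain or CRPS, and it does not describe a maximally treated control arm.

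The reply does not cover CRPS, which has no solicited counterpart in the conservative arm. Nor does it overcome the limits of the two instruments for counting persisting leg pain. The Summary and section 2 present complications as an endpoint for both arms, which invites the comparison of counts that item 3c cannot support.

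**Conclusion.** The point holds in a limited form. As complication items, persisting pain and CRPS are solicited in one arm only, against the stated intention in section 2. The gap is complete for CRPS, apart from spontaneous reports, and partial for pain, where severity is measured equally in both arms but persisting pain in the leg is not counted equally.

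The size cannot be fixed from the documents, which give no rate for either harm. Under equal true rates of 5 to 10% (assumed), a comparison of list counts would have roughly a 30 to 90% chance of a spurious excess after surgery; at 2% the chance is about 1%. This matters only if the counts are compared between arms. The primary endpoint and the sample size are unaffected. It is a low-cost improvement to harm ascertainment, best made while the data can still be collected.

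**What to change.** 1. In section 8.7.13, keep the wound, haematoma and transection items as a description of operated patients.
2. Record persisting pain, reworded to the affected knee or lower leg, and CRPS in both arms at the shared visits from 6 weeks on (6 weeks, 3, 6, 9 and 18 months).
3. Collect both items through unblinded staff so that the assessor stays blind. This could be the treating physician, who already records adverse events, or the contact already foreseen in section 8.4: "A preassessment contact between the patient and an unblinded member should be organized prior to the study assessments".
4. In section 4.3.2 item 3, state that the 10-day surgical check and the operated-area item enter no between-arm count, and that the blinded Stanmore pain section and the EQ-5D pain dimension support the pain comparison.
5. Reconcile the Trial Summary with sections 2, 4.3.2 and 8.7.13 on which complications are recorded, in whom and when. At the same time, settle two loose ends of the 18-month check: section 4.3.2 counts it from surgery while 8.7.13 ties it to the 18-month visit after cross-over, and 8.7.13 gives it to the outcome assessor while the table in 8.8 gives it to the treating physician.

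The cost is two eCRF items at each of five existing visits and some rewording, with no new visit. The drawback is that unblinded patients would report a subjective symptom to unblinded staff, so the new counts need the blinded Stanmore score beside them. If the items are not added, the least that is needed is a statement that these two list items will not be compared between arms.

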The endpoints will be evaluated at fixed time-points: 6 weeks, 3 months, 6 months and 9 months after randomization. Extended follow-up is scheduled 9 months after the primary endpoint is reached i.e. 18 months after randomization. Most trial assessments will be performed by the site-specific blinded researcher, ideally an independent physiotherapist. Patients allocated to the surgical arm of the trial will be evaluated 10 days after neurolysis. A postoperative control is considered standard of care. Sensorimotor function, quality of life and complications will be assessed during this postoperative control. Assessment of MRC-scores for ankle dorsiflexion and ankle eversion is considered standard of care and shall be performed by the treating physician. The treating physician can also assess ankle dorsiflexion strength measured by isometric dynamometry. This cannot be done by the outcome assessor because this would lead to unblinding.

A list of standard assessments (clinical records, considered daily practice = SOC; including motor and sensory function, ability to walk (barefoot), need for orthosis, treatment) will be composed for uniformity across centers. Standard assessments will be conducted at each study visit.

Cross-over is not allowed until the primary endpoint at 9 months is assessed. After the primary endpoint is assessed, cross-over from the conservative arm to surgery is allowed and patients will be treated according to standard of care (decision between treating physician and patient). Extended follow-up for all patients will be organised, 18 months after randomization. All primary and secondary endpoints, with the exception of electrodiagnostics, WPAI and return to work, will be assessed at 18 months. The End-of-Study (EOS) visit will take place at 18 months post-randomization. Cross-over patients will be followed-up as per protocol. All participating physicians and trial sites have the responsibility to guide patients throughout the study visits and are expected to follow protocol and to inform patients in a correct, objective manner. If the TSC documents an unusual high percentage of cross-over in a specific trial site, this trial site can be excluded from the foot drop trial.

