### **8.8 Table of trial procedures**

TABLE OF TRIAL PROCEDURES	SCREENING	RANDOMIZATION !	TREATMENT PERIOD					EXTENDED FU PERIOD CROSS- OVER PATIENTS
			DAY 0	FU 10D (+4D) surgery	FU 6W (+ 1W)	FU 3M (+ 2W)	FU 6M (+ 2W)	FU 18M (+ 3w)
INFORMED CONSENT	TP							
MEDICAL HISTORY	TP							
ELIGIBILITY CRITERIA	TP							
CONTRIBUTING FACTORS	TP							
EDX	TP*					*		*
ISOMETRIC DYNAMOMETRY		BR	TP	BR	BR	BR	BR	BR
6MWT		BR		BR	BR	BR	BR	BR
10MWT		BR		BR	BR	BR	BR	BR
RETURN TO WORK				BR/P				
FUNCTIONAL AMBULATION CATEGORIES		BR		BR	BR	BR	BR	BR
NEED FOR ORTHOSIS		BR		BR	BR	BR	BR	BR
ABILITY TO WALK BAREFOOT		BR		BR	BR	BR	BR	BR
STANMORE QUESTIONNAIRE		BR		BR	BR	BR	BR	BR
EQ5D-5L QUESTIONNAIRE		BR/P	TP/P	BR/P	BR/P	BR/P	BR/P	BR/P
SURGICAL COMPLICATIONS			TP	TP				TP
SENSORY CHANGES	TP	TP/BR	TP	BR	BR	BR	BR	BR
TREATMENT RECORD		BR		BR	BR	BR	BR	BR
WPAI		BR/P		BR/P		BR/P		
ADVERSE EVENTS					TP			
SERIOUS ADVERSE EVENTS					TP			
LEGEND	TP = treating physician; BR = blinded researcher (outcome assessor); bold = standard of care; P = patient (online survey); red = primary endpoint; FU = follow-up; D = days; W = weeks; M= months, YR = year *investigation performed by neurologist / rehabilitation physician, data collection in eCRF by study coordinator Some assessments are done by both the treating physician and blinded researcher to prevent bias/unblinding ! = surgery maximum one week after randomization, preferably within 2 days							

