## 10.3 Data Safety Monitoring Board

Based on the European Medicines Agency (EMA) guidelines on data monitoring committees, the organisation of a Data Safety Monitoring Board is not necessary in the foot drop trial due to following reasons:

1. Peroneal nerve entrapment is no life-threatening disease.
2. The targeted patient population is to be expected to be able to signal any potential harm in an early stage in an appropriate manner.
3. There is no prior knowledge or strong suspicion that a treatment under consideration has the potential to harm patients.
4. The study design gives no reason for setting up a data safety monitoring board
5. The foot drop trial is a study in non-critical indications and both treatment modalities are well characterised, considered daily practice and known for not harming patients.

The independent experts in the TSC will act as an 'extern advisory board' to follow up on possible harm (e.g. related to late cross-over to surgery) and to follow up on blinding and accidental unblinding.

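### The check for surgical complications after cross-over is assigned to the blinded outcome assessor in Section 8.7.13 but to the treating physician in Table 8.8, and its time points do not fit cross-over operations

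*Protocol*

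**What the plan says.** Four places in the Protocol deal with surgical complications.

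- **Section 4.3.2, item 3c** sets the endpoint: "Surgical complications at 10 days, 6 weeks and 18 months after surgery". It is not limited to the randomised surgical arm.
- **The trial summary** groups complications with neurological deficits and counts all their time points from randomisation, with the 10-day one for the surgical group only.
- **Section 8.7.13** says "Surgical complications will be assessed by the treating physician at 10 days and 6 weeks". For operations after cross-over it has one sentence: "After cross-over, surgical complications will be assessed by the outcome assessor at the extended follow-up visit (18 months").
- **Table 8.8** has the row "SURGICAL COMPLICATIONS TP TP TP", with no entry for the blinded researcher. The legend keeps the two roles apart: "TP = treating physician; BR = blinded researcher (outcome assessor").

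Section 5.1 fixes the calendar. "Cross-over is not allowed until the primary endpoint at 9 months is assessed", and "The End-of-Study (EOS) visit will take place at 18 months post-randomization". Section 8.4 forbids participants to talk about their treatment with the outcome assessor and has the operation site covered. Sections 5.1 and 8.4 keep the assessor away from the 10-day post-operative visit because it would unblind them. Section 10.3 does without a data safety monitoring board and asks the independent experts of the Trial Steering Committee to "follow up on possible harm (e.g. related to late cross-over to surgery").

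**The concern.** There are two separate problems.

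The first is blinding. A site cannot follow both the text and the table. If it follows the text, the outcome assessor has to ask about wound infection, dehiscence or haematoma. The sentence applies only after cross-over, so being asked to run the list would itself tell the assessor that the patient was allocated to conservative treatment and later had surgery. Table 8.8 has the same role measure the six-minute walk, the 10-metre walk and dynamometry at that visit. The 18-month values of these secondary endpoints would lose the protection that Section 8.4 sets up.

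The second is ascertainment. Section 8.7.13 says the predefined list exists so that complications are scored uniformly. Six of its ten items concern wound healing, infection, dehiscence or haematoma. In the randomised surgical arm these are looked for at 10 days and 6 weeks. After a cross-over operation they are looked for once, at an interval that depends on when surgery happened to take place. The resulting complication counts do not mean the same thing in the two sets of operations.

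**Working it through.** **Who does the check.** The complication row has three entries, all for the treating physician. The extracted table has lost its 9-month heading and some marks look displaced. The third entry does, however, stand in the same last position as the final entry of the six-minute-walk row, which is the 18-month visit. The conflict over role does not depend on that alignment, because the blinded researcher appears nowhere in the row.

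**When the check can happen.** Inputs:

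- randomised surgery: day 0 to 7 after randomisation (Section 5.1, Table 8.8 footnote)
- cross-over surgery: month 9 or later (Section 5.1)
- last visit: month 18 (Section 5.1), window +3 weeks (Table 8.8)
- one month = 365.25/12 = 30.44 days, so 3 weeks = 0.69 month and 7 days = 0.23 month

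Time since surgery at the last visit = time of last visit − time of surgery.

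*Randomised surgical arm*

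- shortest: 18 − 0.23 = 17.8 months
- longest: 18 + 0.69 − 0 = 18.7 months
- 6-week visit: 6 weeks less 0 to 7 days = 5 to 6 weeks after surgery

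The time points of 3c can be met in this arm.

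*Cross-over operations*

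- longest: 18 − 9 = 9.0 months, or 9.7 months with the +3-week window
- longest if the 9-month visit could also be 3 weeks early (an assumption, since its window is lost in the table): 9.0 + 0.69 + 0.69 = 10.4 months
- shortest: close to 0, if surgery falls just before the last visit
- a check 18 months after the earliest such operation: 9 + 18 = month 27, which is 9 months after the end-of-study visit

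The 10-day and 6-week columns of Table 8.8 follow randomisation and the initial operation. No column follows a cross-over operation. Scheduled list-based checks after cross-over surgery are therefore 1, against 3 named in 3c.

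**How many patients.** The Protocol gives no cross-over rate, so only a ceiling can be shown. It assumes that every conservative-arm patient without a good outcome is operated on, that nobody drops out, and that all 91 surgical-arm patients are operated on.

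| Lowest good-outcome figure used (Table 1) | Cross-overs | Share of all operations |
|---|---|---|
| 53% (absence of gait difficulties, mixed aetiology) | 0.47 × 91 = 42.8, about 43 | 43/(91 + 43) = 32% |
| 64% (lowest MRC-based result) | 0.36 × 91 = 32.8, about 33 | 33/(91 + 33) = 27% |

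The upper end of the reported good-outcome range is 100%, which gives 0 cross-overs. At the complication frequency in Section 1 (7 + 1 of 200 = 4%), 43 operations would yield about 0.04 × 43 = 1.7 events, and 33 about 1.3.

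**The case against.** The best defence is that 3c was never meant for cross-over operations. Randomised surgery follows within a week, so for that arm 18 months after surgery and 18 months after randomisation are nearly the same visit. Section 8.7.13 then gives cross-over its own rule. On this reading nobody planned a month-27 check, and the time origin is loose wording. That is plausible, and it reduces this part to an edit. But 3c states no such limit, and the edit is still needed.

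Four stronger conclusions might be inferred, and the Protocol does not support them.

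- *That the complication endpoint fails as a whole.* The randomised surgical arm can meet it.
- *That cross-over patients have no safety follow-up.* Section 5.1 calls a post-operative control standard of care, Section 10.2 records intervention-related events that participants report with dates, severity and causality, and Table 8.8 has adverse event rows for the treating physician. Serious early events have a route. What is missing is a scheduled check against the list.
- *That the trial loses its test of whether deferring surgery is safe.* Sections 4.1 and 4.2 plan no early-versus-late comparison of complications. Cross-over is decided by patient and physician, so the groups would be self-selected whatever the ascertainment. Section 10.3 mentions late cross-over only as an example within an advisory remit.
- *That about a third of operated patients would go unchecked.* The 32% is a worst case built on a gait outcome in a mixed-aetiology series.

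The blinding harm is also bounded. It concerns the 18-month secondary assessments only, and asking after the walk tests would lessen it. Nothing in Section 8.7.13 requires that order.

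**Conclusion.** The point holds for operations after cross-over. Text and table disagree on who does the 18-month complication check, and the version in the text conflicts with the Protocol's own blinding rules at a visit where secondary gait and strength endpoints are measured. The time origin differs between 3c and the trial summary. For cross-over operations a check 18 months after surgery cannot fall within the trial, and the one scheduled check comes 0 to about 9 months after surgery (9.7 with the visit window).

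The 9-month primary endpoint precedes any permitted cross-over and is untouched, as is the sample size. The number of patients concerned is unknown: 0 to 33 or 43 under the extreme assumptions shown, with only one or two complications expected even then. The contradiction over the assessor stands at any number. The change is worth making because it is cheap and removes an avoidable source of bias, but the main result of the trial does not depend on it.

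**What to change.** Reconcile the trial summary, Section 4.3.2 (3c), Section 8.7.13 and Table 8.8 as follows.

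1. In Section 8.7.13, delete the assignment to the outcome assessor. The treating physician does the 18-month check, as in the table, outside the blinded assessment.
2. In 3c, restate the last time point as 18 months after randomisation, and use the same time origin in the trial summary.
3. For operations after cross-over, record the date of surgery and enter the predefined complication list from whatever standard-of-care post-operative controls fall before the 18-month visit.
4. Report cross-over operations separately, with the time since surgery at each check.

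This changes data recording only. It needs an amendment and reuse of the existing complication form, with a little extra data entry per cross-over patient. Two limits remain. Section 14.2 reports that most surgical patients had a single post-operative evaluation, so a second routine control may not exist for everyone. Operations shortly before the 18-month visit will still have truncated follow-up; one in the last six weeks cannot have a 6-week record within the trial, and the report should say so.
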